6.3 PATIENT SETS ANALYSED

Three patient sets are defined: "all eligible", "all eligible treated", and "restricted"; the following rules are used to assess if a patient is included in an analysis set:

ALL ELIGIBLE: If a patient fulfills all inclusion criteria and no exclusion criteria.

ALL ELIGIBLE TREATED: If a patient fulfills all inclusion criteria and no exclusion criteria and took prescribed treatment at least once.

RESTRICTED: The restricted population is composed of all eligible patients within the trimmed patient set which lie within the region of propensity score overlap (for definition see Section 7). As the propensity score analysis will be based on eligible patients who at least once took the prescribed treatment, the restricted population excludes patients prescribed the treatment but who did not take it.

Number of patients included in the different patient sets will be shown by treatment group.

6.5 POOLING OF CENTRES

Centre will not be used as a variable in any analysis.

6.6 HANDLING OF MISSING DATA AND OUTLIERS

Every reasonable attempt will be undertaken to ensure completeness of data collection.

A review of the data will be performed at the MQRM in order to review reasons and patterns of missing values in the data and to decide on the need for countermeasures.

In general, “unknown” data will be treated as missing. This is because when in the CRF the option “unknown” is given for a question, it is obligatory to tick one optional answer (no missing values). If no “unknown” option is present in the respective question, it is not obligatory to tick one optional answer (leading to missing values if not answered at all).

In the descriptive analyses, unknown values will be treated as an additional category.

Multiple imputations (MI) technique will be used for handling missing value for any of the covariates included in the logistic regression (i.e., alcohol abuse, BMI, Creatinine clearance and smoking status) for the derivation of the average estimated propensity score (ePS). The mean of the ePS for each patient will be estimated from each of the *m* imputed data sets based generally on Rubin’s approach for combining multiple imputed estimates. For example, if 5 imputed data sets are created each patient will have 5 ePS from which a mean ePS would be directly estimated for each patient.

6.7 BASELINE, TIME WINDOWS AND CALCULATED VISITS

The baseline analysis for Objective 2 is cross-sectional in nature. Patients will be assigned to the two treatment groups as described in Section 6.1. For the descriptive analysis, in addition to the data collected at the baseline visit, additional data at hospital discharge or 14 days after the baseline visit (whichever is later) will be collected and summarized descriptively. For the logistic regression analysis to produce estimated propensity scores, data up to the start of dabigatran or VKA treatment will be considered as baseline and will be used as model covariates.

Data from the longitudinal follow-up for collected laboratory data, healthcare resource utilization, and PACT-Q2 will be summarized descriptively at the time points given in [Table 5.3: 2](#). In case time windows will be needed in order to assign observations to visits, observations from 45 days to 134 days after diagnosis will be assigned to month 3, from 135 days to 269 days after diagnosis will be assigned to month 6 and more than 269 days will be assigned to year 1. In case more than one observation is assigned to a certain visit the observation closest to the calculated visit will be assigned. In case two or more observations are on the same day the last will be assigned. Month 3 corresponds to 91 days, month 6 to 182 days, and year 1 to 365 days.

7. PLANNED ANALYSIS

The propensity scores will be estimated after the multiple imputation is performed based on eligible patients who took the prescribed treatment at least once. A logistic regression model will be used to model the probability of receiving dabigatran etexilate in comparison to vitamin K antagonist, i.e. high propensity scores, close to 1, indicate a higher probability of dabigatran use. See Section 7.6 for details.

For the main analysis, only those patients will be included who have a shared range of ePS. This patient set is denoted as the **restricted patient set in the SEAP**. Patients with ePS outside the overlapped ePS range will be trimmed (or excluded).

Safety analyses will be conducted for the all eligible treated patient set.

Summary statistics for continuous variables will include the number of observations (N), mean, standard deviation (SD), minimum, Q1 (25th percentile), median, Q3 (75th percentile), and maximum; tabulations of categorical variables will present all possible categories and will display the number of observations per category as well as percentages. The default precision for percentages should be one decimal place, unless otherwise specified. In general, percentages will be based on the number of patients eligible for the particular analysis, whether they have missing data or not. A category 'Missing' will be displayed whenever at least one patient falls within this category.

Data collected in the baseline eCRFs (informed consent, patient status, demographics, inclusion/exclusion criteria, vital signs and physical assessment, clinical signs and symptoms) will be considered as respective baseline values. Data collected in the hospital discharge related eCRFs will be summarized for the hospital discharge time point. Despite the fact that the analysis is of cross-sectional nature, data collected in eCRFs at hospital discharge will also be summarized in the descriptive analysis.

7.1 DEMOGRAPHIC AND OTHER BASELINE CHARACTERISTICS

Analysis of demographic and other baseline characteristics ([Table 5.3: 1](#)) is defined as a further analysis for Objective 2. Details regarding the further analysis can be found in Section 7.7.

7.2 CONCOMITANT DISEASES AND MEDICATION

Analysis of baseline concomitant diseases, concomitant diseases which started before VTE diagnosis, medical history, and concomitant medication will also be conducted. Concomitant diseases and medical history will be coded using the latest version of MedDRA dictionary, and medications will be coded using the latest WHO drug dictionary preferred name. Both will be summarized using frequencies and percentages for all eligible patients. Patients taking more than one medication in the same preferred name will be counted once.

7.3 TREATMENT ADHERENCE AND PERSISTENCE

Treatment persistence will be assessed as time from treatment onset until permanent treatment discontinuation and summarized descriptively.

Time in therapeutic range (TTR) [3] calculated from INR results obtained at the respective timepoints will be analyzed. For each patient who took prescribed VKA, the TTR percentage will be calculated by linear interpolation between successive test results, and then the number of days in the therapeutic range will be estimated. For the target range 2.0 to 3.0 will be considered.

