### 9.2.4 Visit schedule

Collection of data in the study should be managed during routine practice visits or through telephone contacts with the patient, and follow the schedule in Table [9.2.4:1](#) as closely as possible.

Table 9.2.4:1 Schedule of data collection time-points

	Baseline	At hospital discharge (or 14 days) 	3 months	6 months	12 months
All patients	X	X			
DE or VKA patients followed for 1 year (objective 2 only)	X	X	X	X	X

1. Data will be collected at the date of hospital discharge or at 14 days post diagnosis, whichever is later.

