### 9.3.1.3 Follow-up visit data points

The flowchart ([Table 9.3.1:2](#)) outlines all of the data points to be collected for patients who are followed.

- Type of data collection (i.e., based on routine clinic visit or telephone contact)
- Concomitant diseases (current, any changes)
- Available laboratory data that is associated with outcome events (e.g., CBC for major and clinically relevant non major bleeding events)
- INR for VKA patients
- Anticoagulation treatment (current, any changes (start or stop dates) including adherence, reasons for dose change). Adherence will be assessed using the Morisky Medication Adherence Scale (refer to the [Annex 3.1](#)).
- Changes in concomitant therapies
- Information on any outcome events that may have occurred since the previous visit. If the specific reversal agent for dabigatran is given, information surrounding the clinical circumstances, treatment, and clinical outcome will be collected on the CRF.
- Adverse drug reactions
- PACT-Q2 to be completed by the patient (collection of the PACT-Q2 should occur as close to the data collection time-point as possible). Refer to the [Annex 3.2](#).
- Details of health care resources utilization including:
  - Date, reason and duration of hospitalization occurring
  - Date and reason for visit to ER
  - Need to visit treating physician due to recurrent VTE event, bleeding event or for dose adjustment of anticoagulant therapy
  - For patients treated with VKA only:
    - The number of INR measurements and where the INR blood samples were drawn (e.g., physician's office, anticoagulation clinic, hospital, outpatient laboratory, self-monitoring)
    - At the 3 month data collection time-point *only*, the following details should be collected:
      - The distance traveled to have the INR measured
      - The time spent traveling to have the INR measured
      - If public transportation was used
    - If private transportation was used

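### TTR for the VKA group is interpolated between INRs that, on the natural reading, are study-visit values up to 183 days apart, with no maximum gap and no limit to time on VKA

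*SAP*

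**What the plan says.** SAP Objective 2, section 7.3, states that TTR "calculated from INR results obtained at the respective timepoints will be analyzed". The method is: "For each patient who took prescribed VKA, the TTR percentage will be calculated by linear interpolation between successive test results". The range is fixed: "For the target range 2.0 to 3.0 will be considered". The section does not define the time points. It gives no maximum gap, no minimum number of INRs, and no rule for values taken before VKA starts or after it stops.

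Elsewhere in the documents:

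- **Schedule.** Protocol Table 9.3.1:2 collects laboratory data, where available, at baseline, discharge or 14 days, 3 months, 6 months and 1 year. On the second point, section 9.2.4 says: "Data will be collected at the date of hospital discharge or at 14 days post diagnosis, whichever is later".
- **Days.** SAP section 6.7: "Month 3 corresponds to 91 days, month 6 to 182 days, and year 1 to 365 days". That section and section 7.9.2 tie laboratory summaries, INR included, to scheduled time points.
- **INRs between visits.** Protocol section 9.3.1.3 lists INR as a follow-up item for VKA patients without saying whether one value or all values are wanted. Under resource use it asks separately for "The number of INR measurements and where the INR blood samples were drawn". Section 9.2.4 asks sites to enter data from all usual-practice visits.
- **Time on VKA.** Inclusion criterion 4 requires planned treatment of only 3 months or more. Section 9.2.4 keeps following patients who stop or switch.

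**The concern.** Linear interpolation treats the INR as moving in a straight line from one result to the next. That is tolerable over a few weeks but not over three to six months. Protocol section 7.2 itself describes VKA as having a narrow therapeutic window and being sensitive to diet. A line between two distant values spends more time near the middle of the distribution than the INR does, and the middle is the target range. The method therefore tends to credit time in range that nobody observed.

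TTR is how readers will judge whether the VKA comparator was well managed. Section 7.2 links recurrence and bleeding on VKA to INR control and cites mean TTRs of 57% and 53.7%. An error of several points could change how this study's VKA group compares with those figures.

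**Working it through.** The plan gives no figure for TTR precision, so there is nothing to reproduce. The check takes the visit days from the documents and assumes an INR process.

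**1. Gaps, if only visit INRs are used.** Days 0, 14, 91, 182 and 365 give gaps of 14, 91 − 14 = 77, 182 − 91 = 91, and 365 − 182 = 183 days. A patient on VKA for a year has at most five INRs. One treated for three months has about three.

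**2. One interval by hand (assumed INRs).** With INR 1.5 at month 3 and 3.5 at month 6, the share scored in range is (3.0 − 2.0)/(3.5 − 1.5) = 50%, or 45.5 of 91 days, although neither measurement was in range.

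**3. Values off VKA (assumed INR 1.0 when not anticoagulated).**

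- Before start: INR 1.0 on day 0 and 2.5 on day 14 scores (2.0 − 1.0)/(2.5 − 1.0) = 2/3 of 14 days, about 9 days, as below range.
- After stop: INR 2.5 at month 3, when VKA stops, and 1.0 at month 6 scores (2.5 − 2.0)/1.5 = 1/3 of 91 days, about 30 days, as in range. The other 61 days count as below range. None of these 91 days was on VKA.

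**4. Group mean.** Assume INR is normal with mean 2.45, between-patient SD b and within-patient SD w. Let ρ be the correlation between the two results that bound a gap. With p(s) = Φ((3 − 2.45)/s) − Φ((2 − 2.45)/s):

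- true TTR = p(√(b² + w²))
- interpolated TTR = average over u from 0 to 1 of p(√(b² + w²[(1 − u)² + u² + 2u(1 − u)ρ]))

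Assume a daily autocorrelation of 0.93 to 0.96. Then ρ at 77 days is 0.93^77 = 0.004 to 0.96^77 = 0.04, which is effectively zero. For b = 0 and w = 0.6, true TTR = 0.820 − 0.227 = 59.4%. Halfway across a gap the SD falls to 0.6/√2 = 0.424 and p rises to 75.8%.

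| b | w | True | Interpolated, ρ = 0 | Excess (points) |
|---|---|---|---|---|
| 0 | 0.60 | 59.4% | 69.6% | 10.2 |
| 0.33 | 0.50 | 59.4% | 65.9% | 6.5 |
| 0.45 | 0.40 | 59.2% | 63.0% | 3.8 |

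A different assumed process gives a result inside this range. It uses log-INR with correlation times of 5 to 40 days, between-patient SD 0.10 to 0.15, within-patient SD 0.25 to 0.35, and true TTR 42 to 54%. Visit-only interpolation overstates its mean by about 5 to 8 points.

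**5. Patient level.** Simulating the three settings above (days 14 to 365, 4,000 patients each) gives a visit-only root mean squared error of 22 to 26 points. The log-INR process gives 23 to 26 points, against a true between-patient SD of 11 to 18.

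**6. Alternatives, in the settings of step 4.**

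| Method | Excess in mean (points) | Patient-level RMSE (points) |
|---|---|---|
| Interpolated, visits only | about 4 to 10 | 22 to 26 |
| Interpolated, every 56 days | about 3 to 10 | 13 to 18 |
| Interpolated, every 28 days | about 2 to 9 | 8 to 13 |
| Share of visit INRs in range | within 1 of zero | 20 to 24 |

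Denser INRs mainly improve patient-level accuracy. At 56 days ρ is only 0.02 to 0.10, so most of the bias in the mean remains. The share of INRs in range has no such bias when the timing of the measurement does not depend on the INR. With four values per patient it is still only a group-level summary.

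**The case against.** The strongest reply is that visit-only INRs are an inference. Section 7.3 interpolates between successive results without limiting them to one per visit, and protocol section 9.2.4 asks for data from all usual-practice visits. SAP sections 6.7 and 7.9.2 refer to tables numbered 5.3 that are not in the public text and may define the time points. This stands. It is why the conclusion is conditional and why the first request is to state the source. The separate request for the number of INRs suggests that dated interim values were not all captured, since the count could otherwise be derived, but that is not proof.

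Three stronger readings are tempting, and the documents do not support them.

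- **TTR would be nearly uninformative.** That is close to true for individual patients. The group mean is moderately biased but still carries information. The patient-level correlation with true TTR depends heavily on the assumed process (0.41 to 0.63 in the log-INR process).
- **TTR is the only evidence on the quality of VKA treatment.** INR by visit and persistence are also summarised, and adherence and INR counts are collected.
- **The comparison of dabigatran with VKA is biased.** In the text shown, TTR is not in the propensity model, the Cox covariates or the outcomes, and no analysis classifies patients by TTR.

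**Conclusion.** The point holds, conditionally and at minor severity. On the most natural reading, section 7.3 interpolates across 77 to 183 days with no maximum gap and no restriction to time on VKA. If only visit INRs are used, patient-level TTR is unreliable, with error of about 22 to 26 points. The group mean is overstated by roughly 4 to 10 points before any off-VKA values are counted. Those values push the other way, so a reader should not conclude that the reported mean must be too high. The gaps follow from the documents. The sizes rest on assumed INR processes and are illustrative. What is affected is how VKA control is described and read, not the treatment comparison.

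**What to change.** Amend SAP Objective 2, section 7.3, to:

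1. State whether TTR uses all dated INRs or visit INRs only.
2. Use only INRs between VKA start and VKA stop.
3. If only visit INRs exist, replace the interpolated TTR with the share of visit INRs below, within and above 2.0 to 3.0, reported for the group. Section 7.9.2 already summarises INR by visit, so only the three-way split is new.
4. If dated interim INRs exist, interpolate only across gaps up to a pre-set maximum (for example 8 weeks) and report the proportion of VKA time covered. Show the share of INRs in range beside it, because the cap improves patient-level accuracy but leaves most of the upward bias in the mean.

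The cost is SAP wording and one extra tabulation. Some patients or periods will have no TTR.

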7.4 METHODS ADDRESSING BIAS

See study protocol.

7.5 METHODS ADDRESSING CONFOUNDING/EFFECT MEASURE MODIFICATION

See Section 7.6.

7.6 MAIN ANALYSIS

Analyses for the main outcome events are mainly defined for patients in the restricted patient set and, in some occasions for patients in the eligible patient set who took at least once the treatment. In general, recurrent events will be disregarded for the analyses of the outcomes.

Main outcome events – Incidence rates

For the treatment groups incidence rates with 95% CIs, cumulative risks, and KM curves will be calculated on the eligible patient set. Only patients from the eligible patient set that took the prescribed treatment at least once are considered. Patients who complete the planned anticoagulation treatment prior to one year or discontinue initial anticoagulation treatment permanently will be censored at date of last drug intake + 6 days for both DE and VKA or at first intake of another relevant anticoagulation treatment, whichever occurs first. A patient is considered to have permanently stopped initial anticoagulation treatment if other relevant anticoagulation treatment is initiated or if treatment has been interrupted for more than 30 days.

The main analysis of overall incidence rates with 95% confidence intervals, cumulative risks and KM curves will be repeated for the subgroups defined in Section 6.4. A graphical (forest-plot-like) display will additionally be prepared to summarize the subgroup results per outcome on the eligible patient set. Additional subgroup analyses might be conducted as needed.

For all important main and secondary outcomes for patients initiating VKA at baseline, and patients initiating DE at baseline, incidence rates, cumulative risks with 95%-confidence intervals will be calculated by treatment, and for a graphical comparison Kaplan Meier curves

will be plotted. These statistics will be calculated on the restricted patient set, and patients who never took the prescribed treatment will not be included. For the restricted patient set, as a sensitivity analysis, the calculation of incidence rates and cumulative risks will be performed without censoring at permanent discontinuation (intention to treat (ITT) approach). KM curves will be plotted.

Secondary and further outcome events

For the further outcome events such as Recurrent DVT and/or PE, VTE-related mortality, All-cause mortality, Life-threatening bleeding events, Acute coronary syndrome, and Net clinical benefit, incidence rates, KM estimates and KM curves will be calculated for the eligible patients who took the prescribed treatment at least once for both treatment groups. Additionally, above analyses will be performed on the restricted patient set.

Technical specifications

Incidence rates per 100 patient years with 95%-confidence intervals for important outcome events (single and composite outcome) will be calculated the following way. In addition, these analyses will be done stratified by ongoing chronic antiplatelet treatment at baseline. Recurrent events will be disregarded for calculation of incidence rates. Incidence rate λ is defined as

$$\begin{aligned} \text{Incidence rate } \lambda \left[\frac{1}{100} \text{ pt. yrs} \right]: \\ = 100 * \frac{\text{number of patients with event}}{\frac{1}{365.25} * \sum_{\text{patients}} \text{person time at risk(event)}[\text{days}]} \end{aligned}$$

where the denominator is the patient years under risk. The 2-sided 95% CI of λ will be calculated based on the Poisson distribution and its relationship with the Chi-square distribution according to the following formula [7]

$$[\lambda_{\text{lower}}, \lambda_{\text{upper}}] = [\{0.5 \chi^2(\alpha/2; 2x)\}/n, \{0.5 \chi^2(1 - \alpha/2; 2x + 2)\}/n],$$

where $\chi^2(\gamma, r)$ is the 100 γ th the percentile of a chi-square distribution with r degrees of freedom, n is the patient years under risk for the event, x is the number of patients with event, and α for $(1 - \alpha)\%$ 2-sided CIs.

Cumulative risk is defined as cumulative proportion of patients with event and will be calculated as the Kaplan-Meier estimate for failure. The Kaplan-Meier curve will be plotted. The proportion of patients with event, as well as the proportion of censored patients falling into specified intervals and the Kaplan-Meier estimate for failure will be computed for the following categories:

- ≤ 3 months
- $3 <$ and ≤ 6 months
- $6 <$ and ≤ 12 months
- > 12 months

Distribution and overlap of the ePS between the two groups

The ePS is the probability of a patient being in one of the two treatment groups, conditional on relevant observed baseline variables. For this analysis, the ePS for being in the DE group vs. VKA group will be estimated using the multivariable logistic regression model.

Baseline variables will be included in the model based on their known/suspected association with the main outcome events. As suggested by the literature, only confounders or variables associated with the outcomes will be considered. Table 7.6: 1 summarizes the identified variables to be included in the logistic regression model based on these criteria. In the event of non-convergence, investigations will be done to explore the most likely reason and to aggregate or exclude the responsible variables. Generally, all missing values of variables which will be included in the logistic regression model will be imputed according to Section 6.6.

Table 7.6: 1 Variables for PS model

Variable	Comment	Potential for missing values and implications
Age group	<65, 65 to <75, >=75	Very unlikely
Sex	Male, Female	Rare
BMI	<18.5, 18.5 to <25, 25 to <30, 30 to <35, ≥35, missing	Missing will be imputed
Creatinine clearance	<30, 30 to < 50, 50 to <80, ≥80, missing	Missing will be imputed
Region	Europe, Middle East, North America, Latin America, Asia, Other	Very unlikely
Smoking status	non-smoker, current smoker, past smoker, unknown	Rare – will impute missing and unknown values
Alcohol use	Never, < 1 drink/week, 1-7 drinks/week, ≥8 drinks/week, unknown	Rare – will impute missing and unknown values
Trauma or surgery	True or False (CRF categories, medical history and concomitant diseases will be manually reviewed – 3 month time window)	N/A
Immobilization	True or False (CRF categories, medical history and concomitant diseases will be manually reviewed (past and concomitant))	N/A
Obesity	True or False (CRF categories, medical history and concomitant diseases will be	N/A

	manually reviewed (past and concomitant))	
Thrombophilia	True or False (CRF categories, medical history and concomitant diseases will be manually reviewed (past and concomitant))	N/A
Pregnancy and peri-partum period	True or False (CRF categories, medical history and concomitant diseases will be manually reviewed (3 month time window))	N/A
Concomitant use of aspirin	True or False (concomitant medication and other VTE therapies will be manually reviewed (concomitant))	N/A
Concomitant use of clopidogrel	True or False (concomitant medication and other VTE therapies will be manually reviewed (concomitant))	N/A
Estrogen therapy	True or False (concomitant medication and other VTE therapies will be manually reviewed (3 month time window))	N/A
Concomitant cancer	True or False (CRF categories, medical history and concomitant diseases will be manually reviewed (concomitant))	N/A
Antiphospholipid antibody syndrome	True or False (CRF categories, medical history and concomitant diseases will be manually reviewed (concomitant))	N/A
Polycythemia	True or False (CRF categories, medical history and concomitant diseases will be manually reviewed (concomitant))	N/A
Hypertension	True or False (CRF categories, medical history and concomitant diseases will be manually reviewed (concomitant))	N/A
History of previous VTE	True or False (CRF categories, medical history and concomitant diseases will be manually reviewed (regardless of timing))	N/A
Diabetes mellitus	True or False (CRF categories, medical history and concomitant diseases will be manually reviewed (concomitant))	N/A
Heart failure	True or False (CRF categories, medical history and concomitant diseases will be manually reviewed (regardless of	N/A

	timing))	
History of major bleeding	True or False (medical history and concomitant diseases will be manually reviewed (regardless of timing))	N/A
Stroke	True or False (CRF categories, medical history and concomitant diseases will be manually reviewed (regardless of timing))	N/A
Chronic hepatic disease	True or False (CRF categories, medical history and concomitant diseases will be manually reviewed (concomitant))	N/A
Chronic renal disease	True or False (CRF categories, medical history and concomitant diseases will be manually reviewed (concomitant))	N/A
Index event	DVT, PE, DVT and PE (CRF)	Very unlikely
Prior gastrointestinal bleed	True or False (CRF categories, medical history and concomitant diseases will be manually reviewed (regardless of timing))	N/A
Venous insufficiency or varicose veins	True or False (CRF categories, medical history and concomitant diseases will be manually reviewed (concomitant))	N/A

Overlap of estimated propensity scores

Overlap is the degree to which the ePS of the two treatment groups have a shared range. It is typically best examined graphically but will also be quantified by treatment group using the Kolmogorov Smirnov procedures [4] as a key quantitative indicator of the degree of overlap. To depict overlap in this context, a mirrored bar chart and overlapping line graphs of the estimated ePS of the two groups will be employed. One or both group distributions may be depicted before and after trimming. The same figure will be produced for logit transformed ePS.

In the following if not stated otherwise for all analyses only patients from the restricted patient set are considered.

- 1.) Main analysis of the main outcomes (Major bleeding and clinically relevant non major bleeding, and symptomatic recurrent VTE including VTE-related mortality)

The main analysis will be a PS analysis using overlap weights. A Cox regression model including the overlap weights will be performed. In addition, the main outcomes will be analyzed within the subgroups defined in Section 6.4, when the number of patients per treatment group is at least 500. For the overlap weights analysis each patient in the treatment groups DE and VKA will be weighted proportional to the probability of that

patient being assigned to the opposite treatment group. The weights are called “overlap weights” and are calculated as follows:

$$\begin{aligned} O_{DE} &= 1 - P \\ O_{VKA} &= P \end{aligned}$$

where P is the estimated propensity score of a patient being assigned to the DE treatment group.

To assess baseline imbalance for the overlap weights by ePS, the mean of each covariate of interest will be calculated for patients in each of the treatment groups (DE and VKA). For binary variables, the proportion will be used instead. For categorical variables with more than two categories, dummy binary variables will be derived to represent each category and the proportion calculated for each of the treatments.

The standardized differences will be calculated for the mean for each covariate and the standardized differences (denoted as d) for the mean of a continuous variable is defined [10] as:

$$d = \frac{(\bar{x}_{DE} - \bar{x}_{VKA})}{\sqrt{\frac{s^2_{DE} + s^2_{VKA}}{2}}}$$

where \bar{x}_{DE} and \bar{x}_{VKA} denote the sample mean of the covariate in DE and VKA patients, respectively, while s^2_{DE} and s^2_{VKA} denote the sample variance of the covariate in DE and VKA patients, respectively.

For dichotomous variables, the standardized difference is defined as:

$$d = \frac{(\hat{p}_{DE} - \hat{p}_{VKA})}{\sqrt{\frac{\hat{p}_{DE} * (1 - \hat{p}_{DE}) + \hat{p}_{VKA} * (1 - \hat{p}_{VKA})}{2}}}$$

where \hat{p}_{DE} and \hat{p}_{VKA} denote the proportion or mean of the dichotomous variables in DE and VKA patients, respectively. This approach described above will be repeated for the same covariates of interest after applying the appropriate overlap weight to each patient based on the ePS and will be presented for each covariate. Note that after weighting, the mean will be used instead of the proportion for binary and categorical variables because the weighting applied will make the variables continuous. After weights will have been applied sample means and variances will be substituted by weighted means and weighted sample variances denoted by

$$\bar{x}_{\text{weight}} = \frac{\sum O_i x_i}{\sum O_i}$$

and

$$s^2_{\text{weight}} = \frac{\sum O_i}{(\sum O_i)^2 - \sum O_i^2} * \sum O_i (x_i - \bar{x}_{\text{weight}})^2$$

where O_i is the weight assigned to the i-th patient.

These unadjusted (i.e., prior to using the overlap weights with ePS adjustment) and adjusted (using overlap weights) standardized differences for the mean will be presented for each covariate.

Balance will then be assessed to determine whether the weighted covariates procedure produces standardized differences for the mean and SD closer to zero (indicating a better balance between the study cohorts) than those of unadjusted covariates. Adjusted standardized differences for any covariate that are greater than 0.25 will potentially warrant re-estimation of the ePS model to improve balance.

- 2.) Sensitivity analysis of the main outcomes (Major bleeding and clinically relevant non major bleeding, and symptomatic recurrent VTE including VTE-related mortality)
 - a.) As sensitivity analysis for the comparison of the two treatment groups, dabigatran etexilate and VKA, with regards to the main outcomes a multivariable Cox regression model will be performed. The multivariable Cox regression model will include the variables given in [Table 7.6: 2](#). In case of model convergence issues due to limited number of events, some variables may be removed from the model as deemed necessary.

Table 7.6: 2 Variables for Cox regression model

Variable	Comment	Potential for missing values and implications
Age	continuous	Very unlikely
BMI	continuous	Missing will be imputed
Trauma or surgery	True or False (CRF categories, medical history and concomitant diseases will be manually reviewed – 3 month time window)	N/A
Immobilization	True or False (CRF categories, medical history and concomitant diseases will be manually reviewed (past and concomitant))	N/A
Thrombophilia	True or False (CRF categories, medical history and concomitant diseases will be manually reviewed (past and concomitant))	N/A
Pregnancy and peri-partum period	True or False (CRF categories, medical history and concomitant diseases will be manually reviewed (3 month time window))	N/A

Concomitant use of aspirin	True or False (concomitant medication and other VTE therapies will be manually reviewed (concomitant))	N/A
Concomitant use of clopidogrel	True or False (concomitant medication and other VTE therapies will be manually reviewed (concomitant))	N/A
Estrogen therapy	True or False (concomitant medication and other VTE therapies will be manually reviewed (3 month time window))	N/A
Concomitant cancer	True or False (CRF categories, medical history and concomitant diseases will be manually reviewed (concomitant))	N/A
Hypertension	True or False (CRF categories, medical history and concomitant diseases will be manually reviewed (concomitant))	N/A
History of previous VTE	True or False (CRF categories, medical history and concomitant diseases will be manually reviewed (regardless of timing))	N/A
History of major bleeding or prior gastrointestinal bleed	True or False (medical history and concomitant diseases will be manually reviewed (regardless of timing))	N/A
Chronic renal disease	True or False (CRF categories, medical history and concomitant diseases will be manually reviewed (concomitant))	N/A

Patients who complete the planned anticoagulation treatment prior to one year or discontinue initial anticoagulation treatment permanently will be censored at date of last drug intake + 6 days for both dabigatran etexilate and VKA or at first intake of another relevant anticoagulation treatment, whichever occurs first. A patient is considered to have permanently stopped initial anticoagulation treatment if other relevant anticoagulation treatment is initiated or if treatment has been interrupted for more than 30 days.

Multiple imputation methods (e.g. the fully conditional specification method) will be used to impute both continuous and categorical variables appropriately with arbitrary missing patterns.

- b.) In addition, Cox regression analysis (based on the main analysis model) will be performed without censoring at permanent discontinuation (intention to treat (ITT) approach).

3.) Analyses of secondary and further outcome events

The same Cox regression model as used for the primary outcomes will be used for the secondary and further outcomes, if enough events are reported. The ePS overlap weights analysis on the specific outcome event might be performed for all outcomes.

